During the tapering period, the subjects whose duloxetine dose at discontinuation or completion of the treatment period is 60 mg/day will receive 40 mg/day for one week then 20 mg/day for one week. The subjects whose duloxetine dose at discontinuation or completion of the treatment period is 40 mg/day will receive 20 mg/day for one week.

Administration period:
51 or 52 weeks (50-week treatment period and 1- to 2-week tapering period)

Prohibited drugs and therapies:
Use of the below drugs, or over-the-counter drugs with equivalent effects, is prohibited from Visit 1 (or after completing the observation period at the completion of the tapering period in the preceding study for consecutive subjects) through to Visit 18 (completion of the tapering period):
Prohibited drugs that may affect therapeutic evaluation:
1) Antidepressants

- 2) Anxiolytics
- 3) Soporific agents, other than the “Permitted soporific agents” in Section 6.2.2
- 4) Antipsychotics
- 5) Antiparkinsonian agents
- 6) Anticonvulsants
- 7) Mood-stabilizers (lithium carbonate, carbamazepine, sodium valproate)
- 8) Psychostimulants
- 9) Adrenal corticosteroids (excluding topical agents, such as ear drops, nose drops, eye drops, topical skin formulations, and inhaled formulations).
- 10) Interferon formulations
- 11) Any of the following drugs, which might affect the metabolic/agonistic activities of serotonin or noradrenaline:
 - Cyproheptadine hydrochloride (Periactin®, etc.)
 - Dimetotiazine mesilate (Migristene®)
 - Ifenprodil tartrate (Cerocral®, etc.)
 - 5-HT₃ inhibitors (Zofran®, etc.)
 - 5-HT₄ stimulants (Gasmotin®, etc.)
 - 5-HT_{1B/1D} receptor agonists (Imigran®, etc.)
 - Adrenergic agents (Noradrenaline®, etc.)
- 12) St. John’s wort
- 13) Chinese herbal medicines administered to treat central nervous conditions such as insomnia, neurosis or anxiety.
- 14) Other agents judged to act on the central nervous system, and thus affect therapeutic evaluation.

Prohibited drugs that present safety-related problems:

- 1) MAO inhibitors** (FP®, Azilect®, etc.)

**Administration of these is contraindicated from 14 days before Visit 2 (or after completing the observation period at the completion of the tapering period in the preceding study for consecutive subjects) until 5 days after completion of study drug administration.

- 2) Other investigational drugs

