8.11.1 Adverse events

Adverse events will be classified by system organ class and preferred term, in accordance with MedDRA. Of the adverse events reported using CRFs, TEAEs will be used for safety analysis. TEAEs are defined in Section 7.7.7.11 .

The number of subjects suffering TEAEs, and the numbers suffering death, other serious TEAEs, TEAEs leading to discontinuation of administration, and TEAEs leading to dose reduction will be determined. The TEAE rate and 95% confidence interval will be calculated by the Clopper-Pearson method. The number

of adverse events will also be included. Adverse drug reactions will be summarized in the same manner as TEAEs. Adverse drug reactions are defined in Section 7.7.7.4 .

As summarization of TEAEs by system organ class and preferred term, the number and proportion of subjects suffering these events will be shown. In addition, TEAEs will be summarized by severity, onset timing, and outcome. Adverse drug reactions will be summarized similarly.

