8.1 Compliance

8.1.1 Duration of administration and total dose

The following analyses will be performed for the administration in this study with the safety-analysis set:

- 1) Summary statistics for study drug administration duration will be calculated. Administration duration is defined as follows:

Administration duration (days)

$$= (\text{administration completion date}) - (\text{administration initiation date}) + 1.$$

In addition, times (days) will be converted to week units, and the distributions in the following categories will be summarized: 12 or less weeks; more than 12 to 24 weeks; more than 24 to 50 weeks; and more than 50 weeks.

- 2) Summary statistics will be calculated for the total dose of study drug.
- 3) For the maximum and final doses during the treatment period, the distribution in the following categories will be summarized: 20 mg, 40 mg, 60 mg, 80 mg, and 540 mg.

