8.1.2 Compliance rate

In the safety-analysis set, summary statistics for compliance rate during the treatment period will be calculated. Distribution in the following categories will be summarized: less than 70%, and 70% or more.

Compliance rate is defined as follows:

$$\text{Compliance rate [%]} = \frac{\{ \text{Total Prescription} - 20 \times (\text{Total number of untaken capsules}) \}}{(\text{Total Prescription})} \times 100$$

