- 2) The number of subjects with a given adverse event, the number of cases, and the incidence rate will be determined by adverse event system organ class and preferred term. However, when calculating the number of subjects with a given adverse event and the incidence rate, if the same adverse event occurs more than once with the same subject, these events will be taken to be have affected one subject. Adverse drug reactions will be tabulated similarly.
- 3) With respect to adverse events with an incidence of 2% or more, the number of subjects, number of cases, and incidence rate will be calculated for each adverse event preferred term. Adverse drug reactions will be tabulated similarly.
- 4) The number of subjects and incidence rate will be calculated for each severity and outcome category, by adverse event system organ class and preferred term. If the same adverse event occurs more than once in different categories with the same subject, it will be taken to have occurred once, in the category with the highest of the below priority ranks. Adverse drug reactions will be tabulated similarly.

Priority rank	Survey item category	
	Severity	Outcome
1	Severe	Death
2	Moderate	Recovery with sequelae
3	Mild	No improvement
4		Partial recovery
5		Recovery
6		Unknown

- 5) The number of subjects and the incidence rate will be calculated for each onset timing category (weeks 0 to 8; weeks 8 to 16, weeks 16 to 24, weeks 24 to 32; weeks 32 to 40; weeks 40 to 48; weeks 48 to 50; later than week 50) for adverse events during the treatment period, by system organ class and preferred term. The denominator of the incidence rate will be the number of subjects with administration duration no shorter than the lower limit of each onset time category. The onset timing will be calculated as follows:

Onset timing [day]

$$= (\text{onset date}) - (\text{administration initiation date in the open-label extension study}) + 1$$

When calculating the number of subjects and the incidence rate, if the same adverse event occurs in different categories more than once in the same subject, it will be taken to have occurred with one subject in each of the relevant categories. Adverse drug reactions will be tabulated similarly.

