- 6) With subjects in the safety analysis set who are transferred to the tapering period, adverse events that occur during the tapering period will be summarized. The number of subjects with a given adverse event, the number of cases, and the incidence rate will be determined by adverse event system organ class and preferred term. However, when calculating the number of subjects with a given adverse event and the incidence rate, if the same adverse event occurs more than once with the same subject, these events will be taken to be have affected one subject. Adverse drug reactions will be tabulated similarly.
- 7) With respect to adverse events for which the following standard MedDRA queries (SMQ) are applicable, the number of subjects, number of cases, and incidence rate will be determined by system organ class and preferred term. However, when calculating the number of subjects with a given adverse event and the incidence rate, if the same adverse event occurs more than once with the same subject, these events will be taken to be have affected one subject.

SMQ	Range
Suicide/self-injury	Broad search
Hostility/aggression	Broad search

- 8) The number of subjects and incidence rate will be calculated for each study drug dose category (20 mg, 40 mg, 60 mg, 540 mg) at the onset date of adverse event occurring after the initiation of the open-label extension study, by system organ class and preferred term. When calculating the number of subjects and the incidence rate, if the same adverse event occurs in different categories

more than once in the same subject, it will be taken to have occurred with one subject in each of the relevant categories. Adverse drug reactions will be tabulated similarly.

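### SAP 10.1(5) counts treatment-period events over a duration that appears to include the taper, so its row after week 50 is near zero by construction

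*SAP*

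**What the plan says.** **Numerator.** SAP 10.1 item 5 tabulates incidence by time of onset. The list of rows ends, and the events are defined, as follows: "weeks 48 to 50; later than week 50) for adverse events during the treatment period". Item 6 is a separate table, in which "adverse events that occur during the tapering period will be summarized".

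**Denominator.** For each row it is "the number of subjects with administration duration no shorter than the lower limit of each onset time category".

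**Administration duration.** SAP 8.1.1 item 1 defines it as completion date minus initiation date plus 1. The lead-in is general: "The following analyses will be performed for the administration in this study with the safety-analysis set". The top duration category is more than 50 weeks. Where the SAP means the treatment period alone, it says so: "For the maximum and final doses during the treatment period" in 8.1.1 item 3, and "summary statistics for compliance rate during the treatment period will be calculated" in 8.1.2.

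**Schedule.** The protocol overview gives the administration period as "51 or 52 weeks (50-week treatment period and 1- to 2-week tapering period". Dosing starts the day after Visit 2 (Protocol 5.2). Visit 17, the end of treatment, is nominally day 350, with a window of days 347 to 353 (Protocol Table 7-3, SAP Appendix 2).

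**Protocol analysis text.** Protocol 8.11.1 says that "TEAEs will be summarized by severity, onset timing, and outcome", with no limit to the treatment period.

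**The concern.** An incidence by time of onset can be read only if the people in the denominator could have had a countable event in that row. Here the two parts appear to cover different periods. The numerator stops when treatment ends and the denominator runs on through the taper. The mismatch is greatest in the last row, which opens at the point where the treatment period is due to close.

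Long-term safety is the primary objective, and item 5 is the planned display of how adverse event incidence changes with time on drug. A last row that is almost empty because nothing can fall in it could be taken for evidence of low late risk.

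**Working it through.** **1. The plan's own figures.** 50 + 1 = 51 and 50 + 2 = 52 weeks of administration, that is 357 or 364 days. This agrees with the protocol. The first dose is on study day 1, so onset day (onset date − initiation date + 1) equals study day, and week 50 ends on day 350.

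**2. Days at risk in the last row.** A treatment-period event can fall in this row only if treatment runs past day 350.

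| Visit 17 on day | 347 | 348 | 349 | 350 | 351 | 352 | 353 |
|---|---|---|---|---|---|---|---|
| Treatment days after day 350 | 0 | 0 | 0 | 0 | 1 | 2 | 3 |

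On schedule the row covers 0 days. If Visit 17 were spread evenly over its window (an assumption), the mean is 6/7 = 0.86 day per completer.

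**3. Who enters the last row's denominator, if duration includes the taper.**
- Completers: 135 × 0.75 = 101.25, using the planned 25% dropout. Those who taper have a duration near 357 or 364 days, so they qualify.
- Subjects who stop treatment early but reach 350 days through the taper: stops from day 350 − 7 = 343 (last dose 40 mg/day) or day 350 − 14 = 336 (60 mg/day). With dropout spread evenly over 350 days, withdrawals run at 33.75/350 = 0.096 per day. That adds 0.096 × 7 = 0.68 or 0.096 × 14 = 1.35 subjects.
- Total: 101.9 to 102.6 subjects.

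**4. What the row would show.** Take a constant risk of 10% per 8 weeks, purely for illustration. Then 0 days gives 0%, and 3 days gives 1 − 0.9^(3/56) = 0.6%.

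**5. Earlier rows.** A subject who stops within 7 days (40 mg/day) or 14 days (60 mg/day) before a row's lower limit, and then tapers, is counted in that row with no treatment-period days in it. Under even dropout:
- on treatment at day 56: 135 − 33.75 × 56/350 = 129.6, excess 0.68/129.6 = 0.5%;
- on treatment at day 336: 135 − 33.75 × 336/350 = 102.6, excess 1.35/102.6 = 1.3%.

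**6. If duration excludes the taper.** The denominator rule admits anyone whose duration is at least the lower limit. A subject treated for exactly 350 days still enters the last row with no day at risk in it.

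**7. After the fix.** A single row from week 48 to the end of treatment gives an on-schedule completer 350 − 336 = 14 days at risk. At the same illustrative risk it would show 1 − 0.9^(14/56) = 2.6%.

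**The case against.** The strongest reply is that SAP 8.1.1 never defines the administration completion date and never says that the taper counts. The category for more than 50 weeks does not settle it, since a treatment period ending on days 351 to 353 also exceeds 50 weeks. If item 5 is read as using treatment-period duration throughout, numerator and denominator agree, and the last row is an ordinary overflow row for late Visit 17 dates. This stands in part: inclusion of the taper is a strong inference, not a stated definition. It does not rescue the row, because step 6 applies either way.

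Three further points stand. The maximum of 3 days holds only for visits inside the window. The table is descriptive, with no test or decision rule attached, and its rows already differ in width. SAP section 1 leaves output details to separate mock tables, which might settle the denominator, so it cannot be claimed that two programmers would produce different results.

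A reader might go further and infer that the last row really holds 14 days (7 taper + 7 follow-up, after 40 mg/day) or 21 days (14 + 7, after 60 mg/day), so that the SAP leaves two readings open and discontinuation events are mixed into late-onset incidence. The documents do not support that. Item 5 limits the numerator to the treatment period in terms, and item 6 takes the taper events. Protocol 8.11.1 is broader, but Protocol 8.1 leaves analysis detail to the SAP.

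**Conclusion.** The point holds as a mismatch of periods within one table. On the SAP wording, the row after week 50 has about 100 completers in its denominator, with 0 treatment-period days at risk on schedule and up to 3 for in-window visits. Its rate cannot be interpreted. The dilution of rows from week 8 onward, about 0.5% to 1.3%, is minor.

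This rests on three things: administration duration including the taper (inferred from the general wording of SAP 8.1.1 and the protocol's administration period), the planned 25% dropout spread evenly over 350 days, and all tapers being completed. The 10% risk is illustrative only.

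A reader might conclude that the long-term safety analysis as a whole is compromised. It is not: overall incidence with its confidence interval, the system organ class/preferred term tables and the taper table do not use this denominator. The change is still worth making, because the rule as stated produces an uninformative row under the primary objective and the repair is cheap.

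**What to change.** In SAP 10.1(5), use the same period for numerator and denominator:
- keep the restriction to the treatment period;
- base the denominator on treatment-period duration: last treatment-period administration date − first administration date + 1;
- merge the last two rows into one, labelled *week 48 to end of treatment period*.

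In SAP 8.1.1, state whether administration duration includes the taper.

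The cost is one derived variable and a relabelled row. Protocol 4.5 already has the date of completion or discontinuation of each period recorded in the CRF. Enrolment, data collection and treatment are untouched. The downside is that, among the time-based tables, taper events appear only in item 6.

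If the sponsor instead intends all treatment-emergent events by onset timing, as Protocol 8.11.1 reads, it should remove the treatment-period restriction from item 5, base the denominator on time to the end of adverse event collection (7 days after the last dose, Protocol 7.7.7.2), and label the last row as taper and follow-up. Taper events would then appear in both items 5 and 6, which a footnote should say.

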5.2 Dosage and regimen

All subjects will receive oral duloxetine once daily after breakfast for 51 or 52 weeks (a 50-week treatment period and 1- to 2-week tapering period) from the day after registration (Visit 2). Note that, once or twice between Visits 5 and 17, the subjects should visit the study site without taking a dose to collect a blood sample for pre-dose PK (refer to Section 7.6). Table 5-1 shows the treatment regimens for the study drug. During the treatment period, the subjects will receive duloxetine 20 mg/day for one week then 40 mg/day for one week, and subsequently receive either 40 mg/day or 60 mg/day for 48 weeks as appropriate.

Subjects who complete the treatment period or who withdraw from it during Week 2 or later of treatment period will be transferred to the tapering period. During the tapering period, subjects whose duloxetine dose at discontinuation or completion of the treatment period is 60 mg/day will receive 40 mg/day for one week then 20 mg/day for one week. Subjects whose duloxetine dose at discontinuation or completion of the treatment period is 40 mg/day will receive 20 mg/day for one week. However, tapered administration may be omitted if serious adverse drug reactions occur, there are safety-related problems, or the subject or his/her legal representative refuses the tapered administration.

Table 5-1. Treatment Regimens

Treatment period			Tapering period	
Week 1	Week 2	Weeks 3 - 50	Week 51	Week 52
20 mg/day	40 mg/day	60 mg/day	40 mg/day	20 mg/day
1 x 20 mg LY248686 capsule	2 x 20 mg LY248686 capsule	3 x 20 mg LY248686 capsule	2 x 20 mg LY248686 capsule	1 x 20 mg LY248686 capsule
		40 mg/day	20 mg/day	-
		2 x 20 mg LY248686 capsule	1 x 20 mg LY248686 capsule	-

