5.3 Selection of dose and timing of administration for each subject

During Weeks 3 to 50 of the treatment period, the subjects will receive duloxetine 40 mg/day or 60 mg/day for 48 weeks depending on symptoms. As described in Section 5.2, the tapering period will be 1 or 2 weeks based on the dose at discontinuation or completion of the treatment period.

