9.1.1 Analysis of efficacy endpoints

The following analyses will be performed for the efficacy endpoints.

- 1) Analysis of CDRS-R total score, CGI-S, CDRS-R subscales, and item 13 (suicidal ideation)
 - A) Summary statistics will be calculated at each evaluation time-point in this study.
 - B) Summary statistics for changes from baseline in this study will be calculated at each evaluation time-point and the 95% confidence interval for the mean will be calculated.
 - C) Time-course graph for mean changes (standard deviation) from baseline will be prepared, where the baseline is Visit 2 of this study.
 - D) The CGI-S score category distribution will be summarized at baseline (Visit 2 of this study) and at the final evaluation (week 50 of administration or discontinuation of the treatment period).
- 2) Analysis of CDRS-R total score, CGI-S, CDRS-R subscales, and item 13 (suicidal ideation) from the initiation of the preceding study throughout this study

The following analyses will be performed only in consecutive subjects:

- A) Summary statistics will be calculated at each evaluation time-point in the preceding study and this study.
- B) Summary statistics for changes from baseline in the preceding study will be calculated at each evaluation time-point in the preceding study and this study and the 95% confidence interval for the mean will be calculated.
- C) Time-course graph for mean changes (standard deviation) from baseline in the preceding study will be prepared.
- D) The CGI-S score category distribution will be summarized at baseline in the preceding study and at the final evaluation (week 50 of administration or discontinuation of the treatment period).

10. Safety evaluation

Safety analyses will be performed with the safety-analysis set.

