10.1 Adverse events and adverse drug reactions

Adverse events occurring at or after the initiation of the open-label extension study and continuing from the preceding study will be evaluated. Reported adverse events will be converted to Medical Dictionary for Regulatory Activities (MedDRA) terms, and tabulated by system organ class and preferred term.

- 1) The number of subjects with a given adverse event and the number of cases will be determined, and the incidence rate and 95% confidence interval will be calculated. The incidence rate will be obtained as the proportion of subjects in the analysis set with a specific adverse event, and the confidence interval for the incidence rate will be determined by the Clopper-Pearson method. Totaling will be performed in a similar manner to above with deaths, other serious adverse events, adverse events leading to administration discontinuation, adverse events leading to dose reduction, adverse drug reactions, deaths as adverse drug reactions, other serious adverse drug reactions, adverse drug reactions leading to administration discontinuation, and adverse drug reactions leading to dose reduction. The relevant definitions are shown below.

Death	Adverse event with “Death” as the outcome
Other serious adverse event	Adverse event in the seriousness category “Serious”, except for death
Adverse event leading to administration discontinuation	Adverse event for which the study drug action is “Administration discontinuation”
Adverse event leading to dose reduction	Adverse event for which the study drug action is “Dose reduction”
Adverse drug reaction	Adverse event with the causal relationship with the study drug judged to be other than “Not related”
Death as adverse drug reaction	Death, with the causal relationship with the study drug judged to be other than “Not related”
Other serious adverse drug reaction	Other serious adverse event with the causal relationship with the study drug judged to be other than “Not related”
Adverse drug reaction leading to administration discontinuation	Adverse event leading to administration discontinuation, with the causal relationship with the study drug judged to be other than “Not related”
Adverse drug reaction leading to dose reduction	Adverse event leading to dose reduction, with the causal relationship with the study drug judged to be other than “Not related”

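### SAP 10.1 item 8 reports adverse events by dose at onset without a dose-specific denominator or time at each dose, so its rows differ with exposure and titration even when dose has no effect

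*SAP*

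**What the plan says.** SAP section 10.1, item 8: "The number of subjects and incidence rate will be calculated for each study drug dose category (20 mg, 40 mg, 60 mg, 540 mg". Events are placed by the dose on the onset date and tabulated by system organ class and preferred term. A subject with the same event at two doses counts once in each row. The item gives no denominator.

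The only general definition is in item 1 of the same section: "The incidence rate will be obtained as the proportion of subjects in the analysis set with a specific adverse event". The opening of SAP section 10 adds: "Safety analyses will be performed with the safety-analysis set". By contrast, item 5 of section 10.1 (events by onset window) sets its own denominator, based on how long subjects stayed on drug.

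On exposure, SAP 8.1.1 plans overall duration and also: "Summary statistics will be calculated for the total dose of study drug". It adds: "For the maximum and final doses during the treatment period, the distribution in the following categories will be summarized". Neither SAP 8.1.1 nor Protocol 8.7 summarises time at each dose or the number ever on each dose.

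On the regimen, Protocol 5.2 states: "the subjects will receive duloxetine 20 mg/day for one week then 40 mg/day for one week". For weeks 3 to 50, Protocol 5.3 states: "the subjects will receive duloxetine 40 mg/day or 60 mg/day for 48 weeks depending on symptoms". The taper in Protocol 5.2 adds a final week at 20 mg, preceded by a week at 40 mg for those who end on 60 mg.

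**The concern.** The three scheduled doses have very unequal exposure by design. Everyone passes briefly through 20 mg. Everyone who continues receives 40 mg, for between about 2 and 49 weeks. Only those moved up receive 60 mg, for up to 48 weeks. If each row is a proportion of the same set of subjects, a dose taken for longer, or by more subjects, collects more events for that reason alone.

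Item 8 is the only planned adverse-event table by dose, in a study whose primary objective is long-term safety. Its layout invites comparison across rows. A reader could take a low 20 mg row as good tolerability at initiation and taper, or read a dose pattern into the 40 and 60 mg rows. Either could come purely from the schedule and from how many subjects were moved up.

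**Working it through.** **Inputs from the documents.** 135 registered subjects, 25% dropout and a target of 100 completers (SAP 4.3, Protocol 8.2); the dosing schedule (Protocol 5.2, 5.3). The share moved to 60 mg and the event rates are not in the documents. They are assumed below and varied.

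**The plan's own figures.** 100 / (1 − 0.25) = 133.3, which the plan sets at 135; 135 × 0.75 = 101.25 completers. Schedule for a completer:
- kept at 40 mg: 20 mg for 2 weeks + 40 mg for 49 weeks = 51 weeks;
- moved to 60 mg at week 3: 20 mg for 2 + 40 mg for 2 + 60 mg for 48 = 52 weeks.

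Both match the stated 51 or 52 weeks. The 20 mg share is 2/51 = 3.9% or 2/52 = 3.8%.

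**Step 1: all subjects complete, same rate at every dose.** Take a 20% one-year risk: λ = −ln(0.8)/52 = 0.00429 per week. The chance of an event in w weeks is 1 − exp(−λw): 0.85% for 2 weeks, 18.6% for 48, 19.0% for 49. With share s moved to 60 mg and all subjects as denominator:
- 20 mg row = 0.85%
- 40 mg row = (1 − s) × 19.0% + s × 0.85%
- 60 mg row = s × 18.6%

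| Share on 60 mg | 20 mg | 40 mg | 60 mg |
|---|---|---|---|
| 25% | 0.85% | 14.4% | 4.7% |
| 50% | 0.85% | 9.9% | 9.3% |
| 75% | 0.85% | 5.4% | 14.0% |

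Dose has no effect here, yet the 40:20 ratio runs from 17.0 to 6.3 and the order of 40 and 60 mg reverses.

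**Step 2: with dropout.** Simulation of 400,000 subjects: dropout hazard −ln(0.75)/350 per day, constant event hazard of 0.5 per person-year at every dose, move to 60 mg at day 14, taper for all who stop after day 7. Mean time at 20 mg is 13.9 days, so that row is close to 1 − exp(−0.5 × 13.9/365) = 1.9%. For shares of 20-80%:

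| Denominator | 20 mg | 40 mg | 60 mg |
|---|---|---|---|
| Safety-analysis set | 1.9% | 26.6% down to 8.1% | 6.4% up to 25.8% |
| Ever on that dose | 1.9% | 26.8% down to 8.1% | 32.6% |

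The ever-on-dose denominator removes the effect of titration share from the 60 mg row but leaves the difference in time at dose. If dropouts skip the taper, mean 20 mg time is 12.2 days and that row reads about 1 − exp(−0.5 × 12.2/365) = 1.7%.

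**Step 3: can a real excess at 20 mg be hidden?** With constant hazard, a threefold true rate at 20 mg reads 5.6%. That is still the lowest of the three rows at 20%, 50% and 80% moved up. Now also triple the hazard in days 1-14 and in the taper. All 20 mg time lies in those phases, so its hazard is 9 × 0.5 per year and the row reads 1 − exp(−4.5 × 13.9/365) = 15.8%. That is above the 60 mg row (6.4%) at a 20% share and above the 40 mg row (11.2%) at an 80% share. Whether an excess is hidden therefore depends on timing the documents do not give.

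**Step 4: does person-time repair it?** Use first events at a dose divided by person-time at that dose, stopping at the first event. In Step 1 every row then gives 22.3 per 100 person-years. In Step 2 with a threefold 20 mg hazard, the rates are 1.5 / 0.50 / 0.50 per person-year at 20/40/60 mg for shares of 20%, 50% and 80%, which are the rates put in.

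**Step 5: precision.** 135 × 13.9/365 = 5.1 person-years at 20 mg, about 2.6 each at initiation and taper, and about 5.0 once stopped at first events. Eight first events in 5.0 person-years give 1.6 per year, exact 95% interval 0.7 to 3.2.

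**The case against.** **The denominator is inferred.** Item 8 does not say that the safety-analysis set is the denominator, and SAP section 1 puts the table shells in a separate document, not seen here. This stands. The crude proportion is the likeliest reading, not stated text. But the other natural choice, subjects ever on the dose, leaves most of the distortion (Step 2).

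**Events may cluster exactly where 20 mg is taken.** Protocol 7.7.1 asks for special care in the first 2 weeks, and Protocol 3.1 gives discontinuation events as the reason for the taper. This also stands. A reader might infer that the table will hide an excess at 20 mg. Step 3 shows that this is possible under roughly constant hazard but fails when events cluster strongly at initiation and taper.

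**Time at dose can be worked out from planned outputs.** Mean duration, mean total dose and the scheduled 20 mg time give two equations for mean days at 40 and 60 mg, and SAP 8.1.2 adds: "summary statistics for compliance rate during the treatment period will be calculated". At a 60% share this recovers the model's 127 and 174 days if no dose is missed, or if compliance is equal at all doses and is allowed for. With 5% of doses missed and no allowance it gives 167 and 135, the wrong order. SAP 8.1.1 also leaves open whether total dose means prescribed or taken. This is a rough workaround for the means; it does not replace a reported figure.

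**Little depends on the table.** No dose comparison is among the objectives, Protocol 8.11.1 does not ask for events by dose, and no dose test is planned. True, and it limits the weight of the point. Taper events also have their own table (item 6), though no table isolates week 1.

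**Conclusion.** The point holds as one of analysis and interpretation. Item 8 lacks a dose-specific denominator and the plan lacks time at each dose. At equal true rates its rows would differ several-fold through exposure and the share moved to 60 mg: about 1.9% / 8-27% / 6-26% at 20/40/60 mg, with the 40 and 60 mg order set by the share. Those figures rest on the safety-set reading, constant hazard, 0.5 events per person-year, exponential dropout and a single move at day 14. Later moves would shift time from 60 to 40 mg and leave the 20 mg row unchanged.

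Two stronger readings are not supported. Masking of a 20 mg excess is a possibility, not a finding. Nor does the point undermine the study's safety conclusion: the table is descriptive, and item 1's overall incidence with its Clopper-Pearson interval does not depend on it. Even with person-time the table could not support a dose-response claim, because dose follows symptoms and scheduled 20 mg occurs only at initiation and taper. The change is worth making because it is cheap and the table as worded invites a wrong reading.

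**What to change.** In SAP 10.1 item 8:
- state the denominator for each row (for example, subjects ever on that dose);
- add person-time at each dose, and first events per person-time with person-time at that dose stopped at the first event, for overall and system-organ-class totals;
- show 20 mg at initiation separately from 20 mg in the taper;
- say how events with onset after the last dose, within the 7-day follow-up, are counted;
- footnote that dose followed symptoms and treatment phase, so the rows are not a causal dose comparison.

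The cost is SAP wording and modest programming. Protocol 5.9 already puts administration duration and dosage in the CRF at each visit, and Protocol 7.7.7.1 adds event onset dates. The drawback is imprecision: the 20 mg rates rest on about 5 person-years, half of that per phase, so preferred-term rates by phase would not be worth printing.
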